6.2.1 Screening Evaluation

Consenting Procedure: Patients will be contacted first by phone and, if not available, then by email. The consent process will be conducted by trained study coordinators. The study's purpose and requirements will be explained and the patient will have the opportunity to ask questions and will have time to consider participation. Interested patients will make an appointment to visit the Go Health Clinical Research Unit at Adams School of Dentistry for this study. Study participation. The consent forms will be reviewed and signed by interested patients in person in the Go Health Clinical Research Unit at Adams School of Dentistry prior to study participation. For Spanish speaking patients and/or parents, Spanish forms will be provided and communication will occur through a Spanish translator. All patients are adults and over normal cognitive capacity, and therefore will be able to consent for themselves.

Screening

- At the visit, a consented patient will answer screening questions regarding inclusion and exclusion criteria. Answers will be entered into the CDART research database managed by UNC. A brief oral exam will take place to evaluate for existing severe oral trauma, severe periodontal disease, tumors or infection.
- Prior to finalizing these screening questions, women participants of childbearing potential will be asked to provide a urine sample in the restroom, to undergo a rapid pregnancy test by study personnel. Any pregnant or lactating patients will be excluded.

6.2.2 Enrollment, Baseline, and/or Randomization

Enrollment

Outpatient subjects will be recruited from patients seen in the UNC RDC who have tested positive for SARS-CoV-2+ and consented to be contacted for participation in COVID-19-related research studies. The subjects being approached by phone or email have signed a prior facility consent at the RDC confirming their willingness to share their name and contact information to be contacted for study participation in COVID-19-related research. We will not receive information on subjects that decline this internal consent. A brief review of the patient's Epic chart will take place for medical screening and to identify any missing contact information, as needed. Subjects will be contacted for recruitment by phone and (if unreachable by phone) by secure email by study personnel; patients will have the study rationale and risks explained and will be provided time to ask questions and consider participation.

If patients are interested in participating, appointments will be scheduled for them at the Adams School of Dentistry Go Health Clinical research core. Subjects must be able to attend both visits, to be enrolled. Consent documentation will be signed in person and in private in the Go Health Clinical Research Core. A list of SARS-CoV-2+ subjects that have consented to be contacted for research, will be provided by the RDC clinic, sent via secure UNC servers or secure

UNC email to our research team's clinical coordinator, and this list will include names and contact details (PHI). This list is updated daily and provided to approved research sites, including ours.

Baseline Assessments

In this application, "baseline" refers to the initial saliva sample taken before the participant uses a mouthwash." For this baseline saliva sample, we will measure the salivary viral load and infectivity. The initial brief oral exam will also be a baseline visual inspection.

Randomization

A statistician will create a block randomization schedule and perform these computations; assignments will be placed in organized sequentially numbered opaque envelopes (SNOEs), which are opened as participants are enrolled. Block randomization will provide for group equality. Our sample is limited to adults aged 18-65years, to limit age variability and exclude people at highest risk. We will not preemptively stratify our sample based on our demographic variables (age, gender, race, BMI). However, after we have collected our data, we will check if there is an effect of these demographic features and then include an adjustment if appropriate.

All patients will be consented and then fill out our screening questions for inclusion and exclusion to confirm eligibility prior to being assigned to the randomization schedule. A secondary study coordinator will use a block randomization schedule, organized into SNOEs, to determine the mouthrinse for the next patient, and load it into an unmarked tube. This secondary study coordinator will have no interaction with the patients and the primary study coordinators and lab technicians. The primary study coordinator in charge of collecting the salivary samples will be blinded to the mouthwash solution, as they will be given a pre-aliquoted mouthrinse in an unlabeled storage tube to provide to the patient for the rinse.

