Randomized, double-blind prospective trial to test the efficacy and acceptability of therapeutic, antiseptic mouth rinses to inactivate SARS-CoV-2 virus in saliva of SARS-CoV-2+ patients 18-65 years of age. All mouthrinses are commercially available Colgate products and will be used according to on-label instructions. Patients will be randomized to a mouthrinse and will be asked to give a saliva sample immediately before and after a 30-60 second mouthwash. Saliva samples will be collected from patients at 15-minute intervals thereafter up to one hour (15, 30, 45 and 60 min). The samples will be stored and used for RT-PCR detection of SARS-CoV-2 virus and viral infectivity assays, along with quantitative cytokine and chemokine concentration (pg/mL, Luminex). Patients will also complete a short survey on the taste and experience of using the mouthwash. Peripheral blood will be collected at the end of salivary collection. Participants, except controls, will be provided materials and oral hygiene instruction related to daily use of oral hygiene products provided by the study. In the seven-day period between study visits, participants will be directed to brush with Colgate toothpaste (at least twice per day) and rinse with the Colgate mouthrinse (according to on-label procedures). Controls are not given Colgate products and will be asked to carry out their typical oral hygiene regimen with the products they typically use. All participants will be asked to keep a daily diary of oral hygiene performance, product usage, COVID-19 symptoms and exposures. Daily diary data confirms compliance with oral hygiene protocol, and is needed for data inclusion and analysis, as it relates to secondary and tertiary outcomes for visit 2. Participants will be scheduled to return to the GoHealth Clinical Research Unit at one week after the baseline assessment, during which additional salivary (1 time point, 2 mL of saliva over 5 min, no rinse will occur) and blood samples will be collected. At the conclusion of sample collection, the participant will undergo a periodontal exam. Study participation concludes following the periodontal exam at the end of the second on site study visit. Patients with any periodontitis or gingivitis diagnosis will be informed of their diagnosis and will be referred to an oral healthcare provider for further treatment. Patients' final periodontal status will be a tertiary outcome of the periodontal exam and will be reported as the percentage of participants categorized into each diagnostic group; patients with a periodontal diagnosis will be informed of the findings and will be referred to an oral healthcare provider for further treatment. Participants who provide salivary and blood samples and follow study protocols will receive a \$30 gift card as compensation at the end of visit 1 and \$50 at the end of visit 2. This study involves two 90-minute visits.

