3. STUDY DESIGN

One of the aims of this placebo-controlled, randomized, double-blinded study is to measure the efficacy of antiseptic mouthwashes on reducing SARS-CoV-2 cellular infectivity in COVID+ patient saliva (described above). Asymptomatic and symptomatic SARS-CoV-2+ subjects will be enrolled in the study (according to Inclusion and Exclusion Criteria - Section A.3). Symptomatic SARS-CoV-2+ subjects will be enrolled within 7 days of symptom onset. Subjects' samples are collected in the GoHealth Clinic (Adams School of Dentistry, UNC Chapel Hill, North Carolina, USA). Asymptomatic SARS-CoV-2+ subjects will be enrolled within one week of likely exposure. Study participants who meet all inclusion criteria without any exclusion criteria will be randomized to either an experimental or control group using block randomization.

Participants give a baseline salivary sample (2 mL over 5 min) and then asked to rinse with an mouth rinse for 30-60 sec (on-label instructions) according to the table below:

mouthrinse*	Number of final participants (sample size)	Group
1.5% w/v hydrogen peroxide rinse (Peroxyl)	25**	Experimental
0.12% Chlorhexidine Gluconate (Periogard)	25	Experimental

1 st Peroxyl; 2 nd Periogard [^]	25	Experimental
0.075% Cetylpyridinium Chloride (Colgate Total Zero)	25	Experimental
Sterile Water	25	Control

**All mouthrinses are commercially available in the USA, routinely used in clinical settings, and will be used in an on-label manner.*

***30 participants will be enrolled per regimen to ensure that complete data will be obtained from at least 25 participants per regimen. We assume that ≤ 5 enrollees will drop out or have incomplete data. 30 participants will be enrolled per arm to collect full data sets from 25 participants per arm, assuming some patients will need to be replaced due to inability to complete a visit (missing data).*

[^]For the sequential Peroxyl (1st) and Periogard (2nd) rinses, both oral rinses will be conducted in an on-label fashion. The patient will begin by rinsing with 10 mL of Peroxyl for 60 sec and then expectorate the mouthrinse into an empty tube. Then the patient will rinse with 15 mL of Periogard for 30 seconds and spit this mouthrinse into another empty tube.

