5.2 Handling of Study Interventions

Mouthrinses will be acquired from the following sources:

mouthrinse*	Source: Colgate company providing their commercially available, commercially packaged and ready-for-sale products
1.5% w/v Hydrogen Peroxide rinse	Peroxyl- Colgate
0.12% Chlorhexidine Gluconate	Periogard- Colgate
0.075% Cetylpyridinium Chloride	Colgate Total Zero- Colgate

Sterile water	CVS store
---------------	-----------

**All mouthrinses are commercially available in the USA, routinely used in clinical settings, and will be used in an on-label manner.*

Mouthrinses will be prepared by research study staff in a 50 mL sterile conical tube. The conical tube will be unlabeled so both the participant and study personnel will be blinded to the solution. Any adverse events or protocol deviations will be reported to the UNC IRB. Weekly meetings of the internal quality control committee will allow us to closely monitor such events.

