6.2.3 Blinding

At their onsite visit, subjects will be provided with an unlabeled mouthrinse. If a subject identifies the mouthrinse due to sensation or taste, this will not affect the primary and secondary outcomes as viral load and infectivity are quantitative laboratory assays. The primary study coordinator in charge of collecting the salivary samples will be blinded to the mouthwash solution as well, as they will be given a pre-aliquoted mouthrinse in an unlabeled storage conical to provide to the patient for the rinse. The laboratory technician who will conduct the RT-PCR, viral infectivity and cytokine/chemokine analyte analyses will be blinded to the mouthrinse used prior to the salivary sample collection.

Prior to enrollment of participants, the trial statistician, [name], will prepare the randomization schedule which will be concealed from all other study personnel. To conceal the treatment assignments, [name] will prepare a set of sequentially numbered, opaque envelopes (SNOEs). The SNOEs will be used during recruitment to allocate enrollees to treatment regimens; i.e., for the next patient enrolled, the next envelope will be opened by an approved research staff who has been delegated responsibility for preparing the mouthrinse tubes for the enrollees.

[name] will set up a block randomization schedule that the team will abide by for assignment of enrolled subjects using sequentially numbered, opaque envelopes (SNOEs).

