10. STATISTICAL CONSIDERATIONS

General Design Issues

A double-blinded, randomized controlled trial was chosen as the study design. It allows us to collect human based data on the effects of commercially available mouthrinses on salivary infectivity and viral load. A crossover study was not pursued because the repeated use of different mouthrinses is likely to confound the results. A 1-hour time-course was chosen to correspond with the average length of most dental procedures. Fifteen-minute intervals were chosen to evaluate viral kinetics over time, and to see when infectivity rebounds post-mouthrinse.

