10.2 Sample Size and Randomization

Using data from Meiller *et al.* we calculated power at four time points.¹⁸ Time points included: Post-0 immediately after rinse, Post-30 (30 min post rinse), and Post-60 (60 min post rinse). In addition, we calculated a Post-45, which was the mid-point between 30 and 60 min in the Meiller *et al.* data. Based on this viral study evaluating mouth rinse efficacy against infectivity of Herpes Simplex Virus, an enveloped virus, power calculations were determined to estimate effect size and determine sample size as a function of length of mouth rinse time course.¹⁸ The sample size was justified by a paired t-test on outcomes between time points. With three simultaneous comparisons (t_1-t_0 , t_2-t_0 , t_3-t_0) over 30 min, an $n=16$ sample size can detect the effect size in Cohen's $d=0.7$, which is between medium and large, with 80% power and 0.016 type-I error rate by Bonferroni correction. Therefore, with four simultaneous comparisons (t_0-t_1 , t_0-t_2 , t_0-t_3 , t_0-t_4) the sample size required for each arm is ~25 participants per group to discern oral rinse efficacy at any given time point (minutes post rinse).

[name], who is the statistical consultant on this project, will create a block randomization schedule and perform these computations. SAS Institute (SAS Cary, NC) Proc PLAN will be used to create the randomization schedule. Block randomization will be used to ensure equal and random assignment into each study arm. All patients will be consented and then fill out our screening questions for inclusion and exclusion to confirm eligibility prior to being assigned to the randomization schedule. We will closely collaborate on [name] throughout all stages of this study to ensure statistical rigor.

The researcher responsible for collecting the salivary samples will be blinded to the mouthwash solution, as they will be given a pre-aliquoted mouthrinse in an unlabeled conical tube to provide to the patient for the rinse.

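### The coordinator who collects saliva can recognise the sequential two-rinse arm, so the statement that this person is blinded does not hold for one of the five arms

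*Combined protocol and SAP*

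**What the plan says.** The combined protocol and SAP makes the same blinding claim in several places:

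- Section 6.2.2: the primary coordinator "will be blinded to the mouthwash solution, as they will be given a pre-aliquoted mouthrinse in an unlabeled storage tube". This person gives the rinse to the patient and collects the saliva.
- Section 6.2.3: "The primary study coordinator in charge of collecting the salivary samples will be blinded to the mouthwash solution as well".
- Section 10.2 (Sample Size and Randomization): "The researcher responsible for collecting the salivary samples will be blinded to the mouthwash solution".
- Section 5.2, in general terms: "The conical tube will be unlabeled so both the participant and study personnel will be blinded to the solution".

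The Précis, Section 3 and Section 10 call the trial double-blind without saying which parties are masked; Section 3 has "placebo-controlled, randomized, double-blinded study".

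Section 3, like the adverse-effects table in Section 2.2, describes the sequential arm: "The patient will begin by rinsing with 10 mL of Peroxyl for 60 sec and then expectorate the mouthrinse into an empty tube". A second rinse follows, 15 mL of Periogard for 30 seconds, spat into another tube. Section 5.1 describes a single rinse as the general procedure.

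**The concern.** The collector's blinding rests on one device, the absence of a label on the tube. That conceals a product name. It does not conceal a procedure that differs visibly between arms.

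Two things are at stake. First, a trial report that repeats the protocol would claim more masking at the clinic than the procedure provides. Second, the person who can recognise the arm also takes a decision after randomisation. Under Sections 6.2.5 and 11.3.3, participants who cannot produce enough saliva at the early post-rinse time points are removed, and Section 11.3.3 has the personnel collecting the samples record whether the participant must be replaced. Section 3 then leaves missing data out of the analysis and expects no bias. Section 11.3.3 asks for a note that a volume was insufficient. It does not ask for the measured volume, so even application across arms could not be checked later.

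**Working it through.** No power or error-rate calculation applies. The check sets the rinse procedure beside the blinding statements and counts who is affected.

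**Procedure by arm**

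| | Sequential arm | Four single-rinse arms |
|---|---|---|
| Rinses | 2 (Sections 2.2, 3) | 1 (Section 5.1) |
| Spit tubes described | 2, one per rinse | no second tube |
| Total volume | 10 + 15 = 25 mL | 10 to 20 mL (Section 2.2) |
| Total rinse time | 60 + 30 = 90 s | 30 to 60 s (Sections 2.2, 5.3.2) |

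Both sequential totals lie outside the single-rinse range. Only one regimen has two rinses, so seeing two identifies the arm and both products in it.

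**Is there a safeguard elsewhere?**

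- Dummy second rinse for the other arms, water included: none is described.
- A separate person to supervise the rinse: none is described. Section 6.2.2 keeps the secondary coordinator, who knows the allocation, away from patients and from the primary coordinators.
- Discussion of recognition: Section 6.2.3 considers a participant who identifies the rinse by taste or sensation. It does not consider staff who see the procedure.

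**Share affected**

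- Arms: 1/5 = 20%.
- Planned completers: 25/(5 × 25) = 25/125 = 20%.
- At 30 enrolled per arm (Section 3): 30/(5 × 30) = 30/150 = 20%.

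**Possible cues in other arms**

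- Section 3 treats 10 mL for 60 s (Peroxyl) and 15 mL for 30 s (Periogard) as on-label use. If the single-product arms use the same amounts, volume and time may separate them. The 60-second rinse in Section 5.1, if applied to everyone, would remove the time cue but not the volume cue.
- The Précis gives controls no Colgate products to take home. Before visit 2 this reveals control status to the participant and to any staff who handle the products.

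**What stays masked**

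Section 6.2.3 blinds the technician who runs the RT-PCR, infectivity and cytokine assays. Section 10.5.1 places the primary assays weeks to months after the visit. Recognition in the clinic therefore does not reach the reading of a sample.

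**The case against.** The strongest reply is that this is a wording error with little behind it. Every primary readout is a laboratory assay run by a masked technician. The withdrawal rule is close to objective: a 2 mL sample over 5 minutes, named time points and a marked collection tube. A failure at baseline comes before the rinse and so before any cue. Deficient samples and reasons for discontinuation are documented, and records are reviewed weekly. The acceptability survey is exploratory, and it asks participants about the regimen they experienced. Most of this stands, and it is why the point is minor. It does not make the blinding statements true, and it leaves the measured volume unrecorded.

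A reader might infer more than the documents support:

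- **That the primary outcome is assessed unmasked, or is biased by a known amount.** The technician's masking contradicts the first. The documents give no rate at which the volume rule might be misapplied, so the second cannot be derived.
- **That the double-blind label in the Précis, Section 3 and Section 10 is false as such.** Those places name no masked party. The direct contradiction is with Sections 6.2.2, 6.2.3 and 10.2. Section 5.2 speaks only of study personnel in general.
- **That sequential-arm participants are unmasked.** This depends on whether they are told that others rinse once. The consent text is not among the documents.
- **That only the sequential arm is recognisable.** Saying so would imply that the other four are securely masked, which the volume, time and take-home differences put in doubt.

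**Conclusion.** The point holds as an incorrect blinding statement with a small consequence. The coordinator who collects saliva can recognise the sequential arm from its procedure: 1 of 5 arms, 25 of 125 planned completers, or 30 of 150 at 30 enrolled per arm. These figures count participants whose allocation can be recognised; they do not measure bias.

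The conclusion assumes that the coordinator who hands over the rinse is present while it is used. The documents describe no arrangement to the contrary. Recognition of other arms is possible but not established, except that the lack of take-home products marks the controls before visit 2.

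The primary readouts remain masked. The exposed step is the withdraw-and-replace decision after the rinse, which the plan as written does not make checkable.

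**What to change.** 1. Correct Sections 6.2.2, 6.2.3 and 10.2 (Sample Size and Randomization), with a matching qualifier in Section 5.2. State that the sequential arm is not masked to the collecting coordinator, that other arms may be recognisable from volume, rinse time or take-home products, and that the laboratory technician is masked for all arms. Report masking by role instead of using an unqualified double-blind label.
2. In Sections 6.2.5 and 11.3.3, make the existing 2 mL sample the fixed criterion, and enter the measured volume in CDART at each time point. The marked tubes already allow it to be read.
3. Report withdrawals and replacements after the rinse by arm.

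The cost is wording in a few sections, one CDART field per time point and one table. No extra patients, visits, rinses or assays are needed, and on-label use is unchanged. The downside is that the trial must be described as partly masked at the clinic.

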6.2.3 Blinding

At their onsite visit, subjects will be provided with an unlabeled mouthrinse. If a subject identifies the mouthrinse due to sensation or taste, this will not affect the primary and secondary outcomes as viral load and infectivity are quantitative laboratory assays. The primary study coordinator in charge of collecting the salivary samples will be blinded to the mouthwash solution as well, as they will be given a pre-aliquoted mouthrinse in an unlabeled storage conical to provide to the patient for the rinse. The laboratory technician who will conduct the RT-PCR, viral infectivity and cytokine/chemokine analyte analyses will be blinded to the mouthrinse used prior to the salivary sample collection.

Prior to enrollment of participants, the trial statistician, [name], will prepare the randomization schedule which will be concealed from all other study personnel. To conceal the treatment assignments, [name] will prepare a set of sequentially numbered, opaque envelopes (SNOEs). The SNOEs will be used during recruitment to allocate enrollees to treatment regimens; i.e., for the next patient enrolled, the next envelope will be opened by an approved research staff who has been delegated responsibility for preparing the mouthrinse tubes for the enrollees.

[name] will set up a block randomization schedule that the team will abide by for assignment of enrolled subjects using sequentially numbered, opaque envelopes (SNOEs).

